#### 4.4.1.2.5 **Duration**

Duration is derived from the start and stop dates of the unsolicited non-serious AE provided in the clinical database:

• stop date of unsolicited non-serious AE - start date of unsolicited non-serious AE + 1.

The duration should be considered as missing only if one or both of the start and stop dates of the unsolicited non-serious AE is missing or partially missing.

#### 4.4.1.3 SAEs (including AESIs)

#### 4.4.1.3.1 Intensity

Intensity for SAEs will correspond to the value reported in the CRF.

The maximum intensity corresponds to the highest intensity for a unique term.

#### 4.4.1.3.2 Last Vaccination

Since there is only one vaccination in this study, last vaccination before a SAE is the study vaccination at V01.

#### **4.4.1.3.3** Time of Onset

Time of onset will be computed using the same methodology as for unsolicited non-serious AEs described in Section 4.4.1.2.4.

SAEs (including AESIs) will be analyzed throughout the study using the following periods:

- Within 7 days after vaccination
- Within 30 days after vaccination
- During the study period: from D0 to last visit (i.e., all SAEs [including AESIs] occurred during the study)

An SAE (including AESI) with missing time of onset will be considered to have occurred just after the vaccination indicated by the visit number, so will be included in the safety analysis tables.

Note: SAEs (including AESIs) that occurred before vaccination (negative time of onset) will not be included in analysis, but will be listed separately.

#### 4.4.1.3.4 **Duration**

Duration will be computed using the same methodology as for unsolicited non-serious AEs described in Section 4.4.1.2.5.

# 4.4.1.4 Other Safety Endpoints

#### **4.4.1.4.1 Pregnancy**

Not applicable.

#### **4.4.1.4.2 Action Taken**

This information will be summarized as collected, including missing observations. No derivation or imputation will be done.

# 4.4.1.4.3 Seriousness

This information will be summarized as collected for SAEs. No derivation or imputation will be done.

#### 4.4.1.4.4 **Outcome**

This information will be summarized as collected for Unsolicited non-serious AEs and SAEs. No derivation or imputation will be done.

#### 4.4.1.4.5 Causality

The Investigator will assess the *causal relationship* between each unsolicited systemic AE and the product administered as either *not related* or *related*, based on the following definitions:

- Not related The AE is clearly / most probably caused by other etiologies such as an underlying condition, therapeutic intervention, or concomitant therapy; or the delay between vaccination and the onset of the AE is incompatible with a causal relationship; or the AE started before the first vaccination (screening phase, if applicable)
- Related There is a "reasonable possibility" that the AE was caused by the product administered, meaning that there is evidence or arguments to suggest a causal relationship

Note: By convention, all AEs reported at the injection site (whether solicited or unsolicited) and all solicited systemic AEs are considered to be related to the administered product and therefore are referred to as reactions and do not require the Investigator's opinion on relatedness.

For SAEs only, the causal relationship to study procedures (related/not related to study procedures) will be assessed by both the Investigator and the Sponsor as either *not related* or *related*.

Missing causality (relationship) will be handled as described in Section 5.3.1.2.

#### 4.4.1.4.6 AEs Leading to Study Discontinuation

A flag is available in the clinical database for all AEs in order to identify AEs leading to discontinuation.

In general, the items that are counted are:

- Disposition table: A subject who has, on the termination form, the reason for early termination "Adverse event" checked
- Safety overview table: A subject who has either on the termination form, the reason for early termination "Adverse event" checked or lists an AE on an AE page (solicited, unsolicited, or SAE) that has "Caused study discontinuation" or "Caused study termination" checked that is at least Grade 1 and is within the time period indicated
- System Organ Class/Preferred Term (SOC/PT) table: An event (solicited, unsolicited nonserious, or SAE) that has "Caused study discontinuation" or "Caused study termination" checked that is at least Grade 1 and is within the time period indicated

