#### 4.4.1.2 Unsolicited Non-serious AEs

#### 4.4.1.2.1 Presence

An observation will be considered an event if it has at least a verbatim term and is not a Grade 0 (None) intensity event.

Grade 0 events will not be included in the analysis of the endpoint, and should be included in the listing "Unsolicited non-serious adverse events not included in the safety analysis."

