#### **4.4.1.2.2** Intensity

Intensity for unsolicited non-serious adverse event (AE) will be derived according to the following classification: Grade 0 (None), Grade 1, Grade 2, Grade 3, or Missing (Unknown).

If the unsolicited non-serious AE is measurable and its preferred term is part of the list of solicited reactions, then the measurement is derived based upon and following the same rule than the intensity scales defined in the protocol for that measurable injection site or systemic reaction.

Intensity for the other unsolicited non-serious AEs will correspond to the value reported in the CRF.

The maximum intensity corresponds to the highest intensity for a unique term.

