# **5.3.1.4** Intensity

For solicited reactions, missing intensities will be handled as described in Section 4.4.1.1.1. For unsolicited non-serious AEs, missing intensities will remain missing and will not be imputed.

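### The SAP's Grade 1 threshold for AEs leading to discontinuation drops an unsolicited AE of missing intensity that the SAP elsewhere analyses as an event

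*SAP*

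**What the plan says.** SAP 4.4.1.4.6 starts from a general flag: "A flag is available in the clinical database for all AEs in order to identify AEs leading to discontinuation". It then says, introduced as a general rule, what three tables count.

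- **Disposition table:** a subject whose termination form gives an adverse event as the reason for leaving.
- **Safety overview:** a subject who meets that condition, or who has an AE-page entry (solicited, unsolicited or SAE) with the discontinuation box "checked that is at least Grade 1 and is within the time period indicated".
- **SOC/PT table:** "An event (solicited, unsolicited nonserious, or SAE) that has" the box checked, under the same Grade 1 and time-period conditions. The termination form plays no part here.

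Four other SAP rules bear on intensity.

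- 4.4.1.2.1, unsolicited non-serious AEs: "An observation will be considered an event if it has at least a verbatim term and is not a Grade 0 (None) intensity event". It adds: "Grade 0 events will not be included in the analysis of the endpoint".
- 4.4.1.2.2 lists missing or unknown intensity as a class of its own, separate from Grade 0.
- 5.3.1.4: "For unsolicited non-serious AEs, missing intensities will remain missing and will not be imputed".
- 4.4.1.3.1: "Intensity for SAEs will correspond to the value reported in the CRF". Nothing is said about an SAE whose CRF intensity is blank.

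**The concern.** Two rules in the same SAP use different intensity thresholds for the same record. The event definition removes Grade 0 and keeps everything else. The discontinuation rule keeps Grades 1 to 3 and removes everything else. They disagree only on missing intensity, a class the SAP itself provides for.

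Whether an AE led to early termination is a pre-specified safety parameter (protocol 9.3.2.2 and 12.1.3; SAP 4.3 and 5.1.3). A programmer who follows the SAP literally would list such an AE in the ordinary AE tables and omit it from the SOC/PT discontinuation table. The error can only undercount. It can also leave a child shown as discontinued for an adverse event in one table with no matching event in another.

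**Working it through.** The plan gives no figure for this point, so the check applies the rules to each possible intensity.

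**Unsolicited non-serious AE with a verbatim term, discontinuation box checked and onset within the period**

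| Intensity | Event under 4.4.1.2.1? | Meets the Grade 1 condition of 4.4.1.4.6? | Rules agree? |
|---|---|---|---|
| Grade 0 | No | No | Yes |
| Grade 1, 2 or 3 | Yes | Yes | Yes |
| Missing | Yes | No; 5.3.1.4 bars imputing a grade | **No** |

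**SAEs.** The SOC/PT bullet names SAEs. Section 4.4.1.2.1 is confined to unsolicited non-serious AEs, and the sentence in 5.3.1.4 on leaving missing intensity unimputed is also limited to them. For SAEs there is only 4.4.1.3.1, which takes intensity from the CRF. The SAE endpoint list in SAP 4.3 includes early termination and does not include intensity, and no intensity condition for counting an SAE is stated elsewhere. A flagged SAE with a blank intensity would therefore fail the Grade 1 condition as written. This is an inference from silence; no two rules conflict explicitly.

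**Solicited reactions.** There is no inconsistency. Section 4.4.1.1.1 classes daily intensity as none, Grades 1 to 3, or missing. Section 4.4.1.1.3 turns missing maximum intensity into missing presence, and a subject with no non-missing presence is left out of that endpoint. The Grade 1 condition agrees with this.

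**What each table shows for a child with a flagged unsolicited AE of missing intensity**

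| Termination form | Disposition | Safety overview | SOC/PT discontinuation table |
|---|---|---|---|
| Gives adverse event | Counted | Counted, through the form | Not counted |
| Gives another reason | Not counted | Not counted on this event | Not counted |

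The first row should be the usual one. Protocol 5.2.9 requires a voluntary withdrawal for safety concerns to be recorded as an adverse event, and protocol 5.2.11 places that category first in a list ordered by significance.

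**Size of one lost event.** The input is n = 235, the planned number per group (protocol synopsis; SAP 5.5). The interval is Clopper-Pearson, the SAP's method for safety percentages (5.1.3).

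- Observed rate: 0/235 = 0.0%, against 1/235 = 0.4%.
- Upper 95% limit with 0 events: 1 − 0.025^(1/235) = 1.56%.
- Upper 95% limit with 1 event: the p that solves (1 − p)^235 + 235·p·(1 − p)^234 = 0.025, about 2.35%.

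These figures show what any single event does in a group of this size. They do not estimate how often the rule would apply.

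**The case against.** The strongest case against the point is that the situation will hardly arise and that most of it is already covered. It needs an AE that ends participation in a one-dose study of 30 to 44 days, and a blank intensity on that same AE. Protocol 9.3.2.3.3 requires an intensity for each unsolicited AE, protocol 11.1 requires missing information to be explained, and protocol 13.4.1 requires data queries to be completed before database lock. The protocol's summaries of MET54 and MET51 (1.2.1.1 and 1.2.1.2) report no discontinuation due to an SAE or other AE. All of this stands, and it limits the point to a minor one.

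Second, the three tables draw on different sources and count different units (subjects or events), so they can differ for reasons unrelated to intensity. That is also true. Disagreement between tables is not in itself the defect; the defect is that the event filter conflicts with the SAP's own event definition.

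Third, the section is introduced as a general rule, so the drafters may have meant only to remove Grade 0. That is plausible, but the wording as it stands also removes missing intensity.

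A reader might also infer that the rule breaks a conservative principle running through the SAP, since missing causality counts as related (5.3.1.2) and AEs with missing onset are kept in (4.4.1.2.4). The documents do not support that. A missing immediate field is treated as not immediate (5.3.1.1), and a temperature missing its decimal is completed with zero (4.4.1.1.1). There is no uniform worst-case rule to breach.

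**Conclusion.** The point holds, as a minor one. For unsolicited non-serious AEs the SAP contradicts itself on missing intensity, and the literal reading removes a discontinuation event from the SOC/PT table. For SAEs the same result is inferred from the absence of a rule.

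Two stronger readings are tempting and should not be drawn. One is that the child disappears from the discontinuation results altogether. If the termination form is completed as the protocol directs, the child remains in the disposition and overview tables, and the event remains in the ordinary AE tables. The other is that the conflict extends to all AE types. It does not reach solicited reactions, and for SAEs it is not explicit.

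The likely effect is at most an occasional missing row in one descriptive table. The documents give no rate of missing intensity, so the number of affected events cannot be estimated; it is expected to be very small. No primary or secondary inference is touched. The conclusion assumes that the programming follows the SAP wording literally and that termination forms are coded as protocol 5.2.9 and 5.2.11 direct.

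**What to change.** In both the safety overview and SOC/PT bullets of SAP 4.4.1.4.6, separate the intensity condition by type of event:

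- for unsolicited non-serious AEs and SAEs, the event is not Grade 0, and missing intensity is counted;
- for solicited reactions, the event is at least Grade 1, as now.

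A single not-Grade-0 condition for all events should not be used. Solicited reactions have a class of none and no Grade 0, so a literal filter would let absent reactions through. It would also count solicited reactions of missing intensity, which 4.4.1.1.3 treats as missing presence.

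The cost is one rewritten condition in two bullets and one programming filter. No additional data are needed, and no other analysis changes.

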# 4.4.2 Immunogenicity

# 4.4.2.1 Computed Values for Analysis

In order to appropriately manage extreme values (undetectable responses < the lower limit of quantitation [LLOQ] and  $\ge$  the upper limit of quantitation [ULOQ]) for analysis purposes, the following computational rule is applied to the values provided in the clinical database for each blood sample drawn:

• If a value is < LLOQ, then use the computed value LLOQ/2

- If a value is between  $\geq$  LLOQ and < ULOQ, then use the value
- If a value is  $\geq$  ULOQ, then use the computed value ULOQ

#### **4.4.2.2** Fold-rise

The derived endpoint of fold-rise is computed as follows:

• the ratio of post-vaccination computed value divided by baseline computed value

Note: If baseline or post-vaccination is missing, then fold-rise is missing.

# 4.4.2.3 hSBA Vaccine Seroresponse

The derived seroresponse indicator for hSBA will be "Yes":

- if the pre-vaccination at baseline titer is < 1.8 and the post-vaccination titer  $\ge 1.16$
- or if the pre-vaccination at baseline titer is  $\geq 1:8$  and the post-vaccination is a  $\geq 4$ -fold increase than the pre-vaccination titer.

# 4.4.2.4 rSBA Vaccine Seroresponse

The derived seroresponse indicator for rSBA will be "Yes":

- if the pre-vaccination at baseline titer is < 1:8 and the post-vaccination titer  $\ge 1:32$
- or if the pre-vaccination at baseline titer is  $\geq 1:8$  and the post-vaccination is a  $\geq 4$ -fold increase than the baseline titer at post-vaccination

#### **4.4.2.5** Efficacy

Not applicable

## 4.4.3 Derived Other Variables

#### 4.4.3.1 Age for Demographics

The age of a subject in the study was the calendar age in months at the time of inclusion.

# 4.4.3.2 Duration of a Subject in the Trial

[figure not shown]
The duration of a subject in the study is computed as follows:

Maximum (date of last visit, date of termination) – (date of Visit 1) +1.

# 4.4.3.3 Duration of the Study

The duration of the study is computed as follows:

Maximum of all subjects (date of last visit, date of termination) – Minimum of all subjects (date of Visit 1) + 1.

#### 5.1 Statistical Methods

# 5.1.1 Hypotheses and Statistical Methods for Primary Objectives

The immunogenicity of MenACYW conjugate vaccine serogroup C will be compared to that of Nimenrix® vaccine and to that of NeisVac-C® vaccine using sequential testing approaches. The testing approach will be done in parallel and using a step by step approach for the 2 comparators (3 steps):

# *Nimenrix*®:

If the non-inferiority using seroprotection rates of MenACYW conjugate against Nimenrix® measured by hSBA is demonstrated then the non-inferiority using hSBA GMTs will be tested. If the non-inferiority using hSBA GMTs of MenACYW conjugate against Nimenrix® is demonstrated then the superiority using hSBA GMTs will be tested. If the superiority using hSBA GMTs is demonstrated then the superiority using hSBA seroprotection rates will be tested.

# *NeisVac-C*®:

If the non-inferiority using seroprotection rates of MenACYW conjugate against NeisVac-C® measured by rSBA is demonstrated then the non-inferiority using rSBA GMTs will be tested. And if the non-inferiority using rSBA GMTs is demonstrated then the superiority using rSBA GMTs will be tested.

[figure not shown]

Figure 1: Sequential statistical testing approach for primary objectives

To conclude, non-inferiority using seroprotection rates of MenACYW conjugate against Nimenrix® measured by hSBA or non-inferiority using seroprotection rates of MenACYW conjugate against NeisVac-C® measured by rSBA have to be demonstrated.

# 5.1.1.1 Hypotheses

# Non-Inferiority

A non-inferiority testing approach will be used to compare post-vaccination (i.e., 30 days after the vaccination) seroprotection rates and GMTs of MenACYW conjugate vaccine to that of Nimenrix® and NeisVac-C®, using a two-sided 97.5% Confidence Interval (CI) with the following hypotheses:

For seroprotection rates, the objective is to demonstrate that thirty days after the administration of MenACYW conjugate vaccine, Nimenrix® or NeisVac-C®, the percentage of subjects who achieve an hSBA or rSBA titer  $\geq 1:8$  for meningococcal serogroups C in toddlers who received MenACYW conjugate vaccine (Group 1) is non-inferior to the corresponding percentage in toddlers who received Nimenrix® (Group 2) or NeisVac-C® (Group 3).

This primary objective will be met if the following null hypothesis is rejected for serogroup C:

$$H_0: \pi_{\text{MenACYW}} - \pi_{\textit{Comparator}} \le -0.1$$
  
 $H_1: \pi_{\text{MenACYW}} - \pi_{\textit{Comparator}} > -0.1$ 

where  $\pi_{(MenACYW)}$  and  $\pi_{(comparator)}$  are the percentages of subjects who achieve an hSBA or rSBA titer  $\geq 1:8$  in the MenACYW conjugate vaccine group and the comparator group (Nimenrix® or NeisVac-C®), respectively.

For GMTs, the objective is to demonstrate that thirty days after the administration of MenACYW conjugate vaccine, Nimenrix® or NeisVac-C®, the GMT against meningococcal serogroups C after MenACYW conjugate vaccine (Group 1) is non-inferior to the GMT after Nimenrix® injection in Group 2, or after NeisVac-C® (Group 3).

This objective will be met if the following null-hypothesis is rejected for serogroup C:

$$H_0: GMT_{MenACYW}/GMT_{comparator} \le 1/1.5$$
  
 $H_1: GMT_{MenACYW}/GMT_{comparator} > 1/1.5$ 

# **Superiority**

If the non-inferiority testing succeeds then a superiority approach will be used to compare post-vaccination (i.e., 30 days after the vaccination) seroprotection rates and/or GMTs of MenACYW conjugate vaccine to that of Nimenrix® and NeisVac-C®, using a two-sided 97.5% CI with the following hypotheses:

For seroprotection rates, the objective is to demonstrate that thirty days after the administration of MenACYW conjugate vaccine, Nimenrix® or NeisVac-C®, the percentage of subjects who achieve an hSBA or rSBA titer  $\geq 1:8$  for meningococcal serogroups C in toddlers who received MenACYW conjugate vaccine (Group 1) is superior to the corresponding percentage in toddlers who received Nimenrix® (Group 2) or NeisVac-C® (Group 3).

This objective will be met if the following null hypothesis is rejected for serogroup C:

$$H_0: \pi_{\text{MenACYW}} - \pi_{\textit{Comparator}} \le 0$$
  
 $H_1: \pi_{\text{MenACYW}} - \pi_{\textit{Comparator}} > 0$ 

where  $\pi_{(MenACYW)}$  and  $\pi_{(comparator)}$  are the percentages of subjects who achieve an hSBA or rSBA titer  $\geq 1:8$  in the MenACYW conjugate vaccine group and the comparator group (Nimenrix® or NeisVac-C®), respectively.

For GMTs, the objective is to demonstrate that thirty days after the administration of MenACYW conjugate vaccine, Nimenrix® or NeisVac-C®, the GMT against meningococcal serogroups C after MenACYW conjugate vaccine (Group 1) is superior to the GMT after Nimenrix® injection in Group 2, or after NeisVac-C® (Group 3).

This objective will be met if the following null-hypothesis is rejected for serogroup C:

 $H_0: GMT_{MenACYW} / GMT_{Comparator} \leq 1$ 

 $H_1$ :  $GMT_{MenACYW} / GMT_{Comparator} > 1$ 

with:

- Comparator: Nimenrix® or NeisVac-C®
- $\pi$ : seroprotection rates

#### **5.1.1.2** Statistical Methods

For the seroprotection rates, the 97.5% CI of the difference in proportions will be computed using the Wilson Score method without continuity correction (Newcombe method).

For the GMTs, the two-sided 97.5% CI of the ratio of post-vaccination GMTs will be calculated first using normal approximation of log-transformed titers and then by taking the antilogarithms of the lower and upper limits of the provided 97.5% CI.

The non-inferiority will be demonstrated against seroprotection rates if the null hypothesis is rejected, i.e., if the lower limit of the two-sided 97.5% CI for the difference between the seroprotection rates is > -10%.

The non-inferiority will be demonstrated against GMTs if the null hypothesis is rejected, i.e., lower limit of the two-sided 97.5% CI for the ratio of GMTs > 1/1.5.

The superiority will be demonstrated against seroprotection rates if the null hypothesis is rejected, i.e., if the lower limit of the two-sided 97.5% CI for the difference between the seroprotection rates is > 0%.

The superiority will be demonstrated against GMTs if the null hypothesis is rejected, i.e., lower limit of the two-sided 97.5% CI for the ratio of GMTs > 1.

# 5.1.2 Hypotheses and Statistical Methods for Secondary Objectives

The testing approach will be done in parallel and using a step by step approach for the 2 comparators (3 steps):

[figure not shown]
Nimenrix®:

If the non-inferiority using seroprotection rates of MenACYW conjugate against Nimenrix® measured by rSBA is demonstrated then the non-inferiority using rSBA GMTs will be tested. If the non-inferiority using rSBA GMTs of MenACYW conjugate against Nimenrix® is demonstrated then the superiority using rSBA GMTs will be tested.

#### *NeisVac-C*®:

If the non-inferiority using seroprotection rates of MenACYW conjugate against NeisVac-C® measured by hSBA is demonstrated then the non-inferiority using hSBA GMTs will be tested. And if the non-inferiority using hSBA GMTs is demonstrated then the superiority using hSBA GMTs will be tested.

Figure 2: Sequential statistical testing approach for secondary objectives

To conclude, non-inferiority using seroprotection rates of MenACYW conjugate vaccine against Nimenrix® measured by rSBA or non-inferiority using seroprotection rates of MenACYW conjugate vaccine against NeisVac-C® measured by hSBA have to be demonstrated.

# 5.1.2.1 Hypotheses

A similar statistical approach as for the primary objective will be used considering the rSBA antibody titers for Nimenrix® and hSBA antibody titers for NeisVac-C®.

Non-inferiority hypotheses will be similar as for the primary objective. Superiority will be tested only on GMTs, not on seroprotection rates.

